A pilot study in cSCC was presented at the 44th European Society of Medical Oncology in 2019 using 2 doses of neoadjuvant cemiplimab for patients with Stage 3 and 4 cSCC of the head and neck. (NCT03565783) In this study of 20 patients, the treatment was well tolerated with no grade 3 or 4 AEs. 55% of patients achieved a pathological complete response and 15% of patients achieve a major pathological response (<10% viable tumor). All patients were able to proceed with anticipated curative surgical resection. (Gross)

In addition to this trial, other studies have shown a neoadjuvant approach is feasible with cutaneous malignancies and can result in decreased surgical defects. Blank et. al. examined neoadjuvant versus adjuvant ipilimumab plus nivolumab in macroscopic stage III melanoma and found that all of the patients in the neoadjuvant treatment arm were able to undergo the anticipated surgery. Of the 9 patients evaluable in the neoadjuvant arm, 78% achieved a significant pathological response and majority had a decrease in lesion size. In a trial of vismodegib used in a neoadjuvant fashion prior to treatment of high-risk basal cell carcinoma, surgical defect size was reduced by 27% in patients who were able to complete 3 months of treatment with all patients able to complete surgical resection. (Ally)

The risks of this trial, similar to other neoadjuvant trials, include the possibility of disease progression resulting in either a more extensive resection than initially anticipated or loss of opportunity for curative surgery. Encouraging data from a preliminary study (NCT03565783, Gross) showed that the risk of this is likely low and worth the potential opportunity to reduce lesion size. This risk will be minimized by careful monitoring of visible lesions following each cycle, and also includes an additional imaging study after the second dose of atezolizumab to check for radiographic evidence of disease progression.

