#### **4.5 Tumor and Response Evaluations**

Patients will undergo tumor assessments at baseline and according to the schedule specified in the study calendar (section 9). These are clinical observations and judgements used by the investigator and medical team of the patient's clinical status to determine the appropriateness of continuing study intervention. At the investigator's discretion, tumor assessments may be repeated at any time if progressive disease is suspected. All tumor assessments following surgical resection will be per standards of care.

All measurable and evaluable lesions should be assessed and documented at screening. Tumor assessments performed as standard of care prior to obtaining informed consent and within 28 days prior to initiation of study treatment do not have to be repeated at screening.

Overall response at a single timepoint will be assessed by the investigator using RECIST v1.1 (see Appendix F) at baseline and Day 38 ( $\pm 4$  days).

Screening assessments must include CT scans (with IV contrast) or MRI scans of the primary site (if present), regional lymphatics, thorax, and depending on the location of the tumor, may include other relevant anatomy. PET/CT or CT of the thorax are appropriate preoperative workup; however, cannot substitute for either the CT or MRI of the primary site if present, and regional lymphatics. CT of the thorax need not be repeated after baseline unless there is clinical indication. If a CT scan with contrast is contraindicated (e.g., in patients with impaired renal clearance), a non-contrast CT scan of the chest may be performed and MRI scans of regional lymphatics and, if applicable, primary site should be performed. The same radiographic procedures used to assess disease sites at screening should be used for subsequent tumor assessments (e.g., the same contrast protocol for CT scans) as listed in section 9. At the investigator's discretion, other methods of assessment of measurable disease as per RECIST v1.1 may be used.

If a CT scan for primary tumor assessment is performed in a positron emission tomography (PET)/CT scanner, all efforts should be made so the CT acquisition is consistent with the standards for a full-contrast diagnostic CT scan.

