## **4.8 Criteria for Removal from Study**

Patients must permanently discontinue study treatment (atezolizumab) if they experience any of the following:

- Intolerable toxicity related to study treatment, including development of an immune-mediated adverse event determined by the investigator to be unacceptable given the individual patient's potential response to therapy and severity of the event
- Any medical condition that may jeopardize the patient's safety if he or she continues study treatment
- Investigator determines it is in the best interest of the patient
- Use of another non-protocol anti-cancer therapy
- Pregnancy
- Loss of clinical benefit as determined by the investigator after an integrated assessment of radiographic and biochemical data, local biopsy results (if available), and clinical status (e.g., symptomatic deterioration such as pain secondary to disease)

The primary reason for study treatment discontinuation should be documented in the patient's medical records.

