### **5. INVESTIGATIONAL AGENT/DEVICE/PROCEDURE INFORMATION**

#### **5.1 Investigational Agent/Device/Procedure**

The investigational medicinal product (IMP) for this study is atezolizumab.

Atezolizumab will be administered by IV infusion at a fixed dose of 1200 mg on Day 1 (+/- 3 days) of each 21-day cycle for a total of 3 doses prior to surgery, unless there is clinical or radiographic evidence of disease progression.

Administration of atezolizumab will be performed in a monitored setting where there is immediate access to trained personnel and adequate equipment and medicine to manage potentially serious reactions. For anaphylaxis precautions, see Appendix H.

Atezolizumab infusions will be administered per the instructions outlined in Table 1.

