- f Record abnormalities observed at baseline in the patient's medical records. At subsequent visits, record new or worsened clinically significant abnormalities in the patient's medical records.
- g Perform a limited, symptom-directed examination at specified timepoints and as clinically indicated at other timepoints. Record new or worsened clinically significant abnormalities in the patient's medical records.

---

- h ECG recordings will be obtained during screening and as clinically indicated at other timepoints.
- i Hematology includes WBC count, hemoglobin, hematocrit, platelet count, differential count.
- j Screening laboratory test results must be obtained within 28 days prior to initiation of study treatment.
- k If screening laboratory assessments were performed within 96 hours prior to Day 1 of Cycle 1, they do not have to be repeated.
- l Chemistry panel (serum or plasma) includes sodium, potassium, chloride, bicarbonate, glucose, BUN or urea, creatinine, total protein, albumin, calcium, total bilirubin, alkaline phosphatase, ALT, AST.
- m All women of childbearing potential will have a serum pregnancy test at screening, within 28 days prior to initiation of study treatment.
- n Past TSH lab value may be used for screening if collected within 6 weeks prior to the first administration of atezolizumab.
- o Urinalysis includes pH, specific gravity, glucose, protein, ketones, and blood
- p Baseline imaging with CT or MRI of primary site (if present) and regional lymphatics; CT Chest or PET scan will be performed only if scans were not previously performed within 28 days of screening assessment. The same radiographic modality used to assess disease sites at screening should be used for subsequent tumor assessment at baseline and after cycle 2. **RECIST measurements are only required at baseline, after cycle 2, and ORR can be assessed after cycle 2/surgery.**
- q See Section 4.6 for details on exploratory research
- r All measurable and evaluable lesions should be assessed and documented at screening. Tumor assessments performed as standard of care prior to obtaining informed consent and within 28 days prior to initiation of study treatment do not have to be repeated at screening.

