#### **11.4 Compliance with Laws and Regulations**

Patients who comply with the requirements of the protocol, are tolerating study treatment, and may be receiving benefit will be offered dosing beyond Cycle 1 at the investigator's discretion after a careful assessment and thorough discussion of the potential risks and benefits of continued treatment with the patient. Such patients may have the option to receive MPDL3280A treatment as long as they continue to experience clinical benefit in the opinion of the investigator until the earlier of unacceptable toxicity, symptomatic deterioration attributed to disease progression, or any of the other reasons for treatment discontinuation listed in Section 4.8.

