## NEW LESIONS

The appearance of new malignant lesions denotes disease progression; therefore, some comments on detection of new lesions are important. There are no specific criteria for the identification of new radiographic lesions; however, the finding of a new lesion should be unequivocal, that is, not attributable to differences in scanning technique, change in imaging modality, or findings thought to represent something other than tumor (for example, some "new" bone lesions may be simply healing or flare of preexisting lesions). This is particularly important when the patient's baseline lesions show PR or CR. For example, necrosis of a liver lesion may be reported on a CT scan report as a "new" cystic lesion, which it is not.

A lesion identified during the study in an anatomical location that was not scanned at baseline is considered a new lesion and will indicate disease progression.

If a new lesion is equivocal, for example because of its small size, continued therapy and follow-up evaluation will clarify if it represents truly new disease. If repeat scans confirm there is definitely a new lesion, progression should be declared using the date of the initial scan.

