## SPECIAL NOTES ON RESPONSE ASSESSMENT

Patients with a global deterioration in health status requiring discontinuation of treatment without objective evidence of disease progression at that time should be reported as "symptomatic deterioration." Every effort should be made to document objective progression even after discontinuation of treatment. Symptomatic deterioration is not a descriptor of an objective response; it is a reason for stopping study therapy. The objective response status of such patients is to be determined by evaluation of target and non-target lesions as shown in [Table 1](#).

For equivocal findings of progression (e.g., very small and uncertain new lesions; cystic changes or necrosis in existing lesions), treatment may continue until the next scheduled assessment. If at the next scheduled assessment, progression is confirmed, the date of progression should be the earlier date when progression was suspected.

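### Progression at the Day 38 scan has no single consequence: sections differ on whether dosing stops, equivocal findings have no scheduled resolution, and 12.1 scores the patient differently from 1.1 and 10.1

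*Combined protocol and SAP*

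**What the plan says.** **Dosing.** The synopsis, 2.4 and 5.1 share one rule: atezolizumab is given "for a total of 3 doses prior to surgery, unless there is clinical or radiographic evidence of disease progression". Section 4.8 lists events after which treatment must stop for good. Progression is not among them; the nearest item is "Loss of clinical benefit as determined by the investigator after an integrated assessment of radiographic and biochemical data" and other information. Section 11.4 lets patients who may be benefiting continue at the investigator's discretion "until the earlier of unacceptable toxicity, symptomatic deterioration attributed to disease progression", or another reason listed in 4.8. Section 4.5 describes tumor assessments as judgements used "to determine the appropriateness of continuing study intervention".

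**Equivocal findings.** Appendix F (Special Notes on Response Assessment) says that for these "treatment may continue until the next scheduled assessment", with progression back-dated if it is then confirmed. Its New Lesions paragraph says of an equivocal new lesion that "continued therapy and follow-up evaluation will clarify if it represents truly new disease", and back-dates progression once repeat scans confirm it.

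**Schedule.** Section 4.5 sets RECIST assessments at baseline and Day 38 (±4 days). Footnotes p and s of the Section 9 calendar state that "RECIST measurements are only required at baseline, after cycle 2", and add that response can be assessed after cycle 2 or surgery.

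**Purpose of the scan.** Section 2.3 names two risks, a larger resection and loss of curative surgery. It offers as mitigation "an additional imaging study after the second dose of atezolizumab to check for radiographic evidence of disease progression".

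**Scoring.** Sections 1.1 and 10.1 classify a patient with progression during the neoadjuvant phase as non-feasible. Section 12.1 declares feasibility if 17 or more patients finish treatment and go on to resection. It declares the opposite if 4 or more cannot finish because of toxicity or progression, or are unresectable at surgery. Sections 7.2 and 12.3 stop the study at 4 failures.

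**The concern.** A scan offered as a safeguard should lead to a defined action. Here the action depends on which section the investigator reads, and for an equivocal finding Appendix F points to a later reading that the calendar does not contain.

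Two things are at stake. The first is consistency of handling: two patients with the same Day 38 scan could be treated differently, each within the protocol. The second is the primary outcome. With 20 patients and a margin of three failures, the scoring of a single patient who progresses but completes treatment and surgery can decide both the feasibility conclusion and whether the study stops early.

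**Working it through.** **1. Definite progression.** Take an asymptomatic patient whose sum of target diameters has risen by 22% and 6 mm at Day 38. Appendix F requires at least 20% and at least 5 mm, so this is progressive disease.

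| Section | Consequence for dose 3 |
|---|---|
| Synopsis, 2.4, 5.1 | Not given |
| 4.8 | Progression not named; stopping turns on the investigator's judgement of benefit |
| 11.4 | May be given if the investigator sees benefit; only symptomatic deterioration is tied to progression |
| 4.5 | The result informs a judgement |
| Calendar footnote b | The visit showing progression may serve as the discontinuation visit (permissive) |

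The direct conflict is between 5.1 and 11.4. Section 4.8 differs from 5.1 by omission, but 11.4 refers back to 4.8, so a reader following those two never meets a radiographic stop.

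**2. Equivocal progression.** After Day 38 the calendar schedules tumor assessments at Day 42 (before dosing) and at surgery. Footnote s describes the per-cycle assessments as clinical. The imaging rows are marked only at screening and, for the primary site and regional lymphatics, at Day 38. Section 12.6 says lesions that are not visible are assessed for response only after cycle 2. Appendix F rules out histology for objective tumor evaluation, so the surgical specimen cannot supply the RECIST confirmation. A visible lesion can be re-measured clinically at Day 42. An equivocal finding in a lesion that is not visible has no scheduled reading that could confirm it, and back-dating then depends on a discretionary repeat.

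**3. Scan-to-surgery interval if dose 3 is given.** Inputs: scan Day 38 ± 4, dose 3 Day 42 ± 3, surgery 2 to 4 weeks after Cycle 3, taken here as after dose 3.

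- Nominal: 42 + 14 = Day 56 and 42 + 28 = Day 70. Subtracting 38 gives 18 to 32 days.
- With windows: the shortest case has scan and dose on the same day (possible on Days 39 to 42, scan first), giving 14 days. The longest is scan Day 34, dose Day 45, surgery Day 73, giving 73 − 34 = 39 days.
- If the surgery window starts at the end of the 21-day cycle (assumption): 42 + 21 + 14 − 38 = 39 and 42 + 21 + 28 − 38 = 53 days, nominally.

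**4. Scoring.** Suppose the patient in step 1 receives dose 3 and is resected.

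- Under 1.1 and 10.1: progression during treatment, so a failure.
- Under the literal wording of 12.1: finished treatment and was resectable, so not among the failures and able to count toward the 17.

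The margin is 20 − 17 = 3 failures. With three others already failed, this patient makes the result 17 of 20 or 16 of 20, and 20 − 16 = 4 reaches the stopping limit.

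**5. Size for the feasibility rule.** The plan's own figure first: with N = 20, null 50% and a 5% test, the exact critical value is 15 or more (one-sided alpha 0.0207), and power at 80% is 0.804. That reproduces the stated power of at least 80%. The operating rule in 12.1 is 17 or more, so for scoring I use P(X ≥ 17), X ~ Binomial(20, p). At p = 0.85 the terms for 17, 18, 19 and 20 are 0.243 + 0.229 + 0.137 + 0.039 = 0.648.

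Assume the rate is 0.85, the plan's expected value, when patients who progress but complete count as successes.

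| Share of such patients (assumption) | Rate if scored as failures | P(17 or more) |
|---|---|---|
| 0% | 0.85 | 0.648 |
| 5% | 0.80 | 0.411 |
| 10% | 0.75 | 0.225 |

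The documents give no estimate of this share.

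**The case against.** The best defence is that 5.1 governs. Its rule appears three times in the same words, 4.8 never claims to be exhaustive or to permit dosing after progression, and footnote b expects a visit showing progression to be usable as the discontinuation visit. Against 4.8 alone this stands: a reader might infer that 4.8 flatly contradicts 5.1, but the two can be applied together. It does not dispose of 11.4, which is in the current text and gives its own conditions for continuing. That section sits under a compliance heading and describes open-ended dosing that does not fit a three-dose course. It may be carried-over text, but it is in force.

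On Appendix F, a reader might infer that an equivocal finding can never be resolved. The documents do not support that. Section 4.5 allows a repeat assessment at any time if progression is suspected, and footnotes p and s leave room for a later response assessment. Also, the next scheduled assessment after Day 38 is the pre-dose one at Day 42, so the deferral does not by itself authorise dose 3. What remains is that no later scan or RECIST reading is scheduled or required.

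On the outcome, a reader might infer that giving dose 3 turns a patient with definite progression into a success. Under 1.1 and 10.1 it does not; only the wording of 12.1 opens that route.

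The 18 to 32 days could be taken for a delay caused by continuing. It is only the time from scan to surgery, because the documents give no surgery date for a patient stopped at Day 38 to compare it with. Nor can it be said that patients were told the scan protects them: 2.3 is protocol rationale, and the consent pages are not available.

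**Conclusion.** The point holds. The synopsis, 2.4 and 5.1 end dosing at progression; 11.4, with 4.8 behind it, leaves dosing after radiographic progression to judgement. The Appendix F deferral does not fit a calendar with no scan or required RECIST reading after Day 38, and the gap is confined to equivocal findings in lesions that are not visible. Sections 1.1 and 10.1 disagree with 12.1 on a patient who progresses, completes three doses and is resected.

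One such patient can move the result from 17 to 16 of 20 or reach the four-failure stop. On the assumption that such patients are 5% to 10% of the total and that the rate counting them as successes is 0.85, the chance of declaring feasibility falls from 0.648 to between 0.411 and 0.225 when they are scored as failures. The textual conflict does not depend on those shares. No view is taken on which clinical rule is right.

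**What to change.** 1. Reconcile the synopsis, 2.4, 4.8, 5.1, 11.4 and the two Appendix F passages (New Lesions; Special Notes on Response Assessment) into one statement of what follows definite and equivocal progression at Day 38, and cross-refer to it from each place. The choice of rule belongs to the sponsor's clinicians.
2. Adapt the Appendix F text on the next scheduled assessment, repeat scans and back-dating to the schedule this study actually has.
3. Align 12.1 with 1.1 and 10.1, and apply the same definition to the stopping counts in 7.2 and 12.3. State how definite progression is scored when the patient completes treatment and surgery, and how an equivocal Day 38 reading is scored with and without a later confirming assessment.

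The cost is protocol wording only, with no added scan, visit or patient.

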**Table 1 Administration of First and Subsequent Atezolizumab Infusions**

First Infusion	Subsequent Infusions

• No premedication is permitted prior to the atezolizumab infusion.

• Vital signs (pulse rate, respiratory rate, blood pressure, and temperature) should be measured within 60 minutes prior to the infusion.

• Atezolizumab should be infused over 60 (<math>\pm 15</math>) minutes.

• If clinically indicated, vital signs should be measured every 15 (<math>\pm 5</math>) minutes during the infusion and at 30 (<math>\pm 10</math>) minutes after the infusion.

• Patients should be informed about the possibility of delayed post-infusion symptoms and instructed to contact their study physician if they develop such symptoms.

	

• If the patient experienced an infusion-related reaction with any previous infusion, premedication with antihistamines, antipyretics, and/or analgesics may be administered for subsequent doses at the discretion of the investigator.

• Vital signs should be measured within 60 minutes prior to the infusion.

• Atezolizumab should be infused over 30 (<math>\pm 10</math>) minutes if the previous infusion was tolerated without an infusion-related reaction, or 60 (<math>\pm 15</math>) minutes if the patient experienced an infusion-related reaction with the previous infusion.

• If clinically indicated, vital signs should be measured during the infusion and at 30 (<math>\pm 10</math>) minutes after the infusion.

Refer to the pharmacy manual for detailed instructions on drug preparation, storage, and administration.

Guidelines for medical management of infusion-related reactions (IRRs) are provided in Appendix H.

Any overdose or incorrect administration of atezolizumab should be noted in the patient's medical records and reported according to Section 7.5 (Special Situations Reports). Adverse events associated with an overdose or incorrect administration of any of the study treatments should be recorded in the patient's medical records.

Guidelines for discontinuation for patients who experience adverse events are provided in Appendix I.

## 5.2 Availability

Genentech will provide atezolizumab.

The atezolizumab 1200 mg drug product will be supplied in a single-use, 20-mL USP/Ph. Eur. Type 1 glass vial as a colorless to slightly yellow, sterile, preservative-free clear liquid solution intended for IV administration. The vial is designed to deliver 20 mL (1200 mg) of atezolizumab solution but may contain more than the stated volume to enable delivery of the entire 20-mL volume.

For information on the formulation and handling of atezolizumab, see the Atezolizumab Investigator's Brochure.

